## **Amendment 01**

### **Amendment rationale**

Subsequent to the acquisition of GlaxoSmithKline (GSK) compound **SB-497115**, the purpose of this protocol Amendment **01** is to:

- Delete or replace references to GSK or its staff with that of Novartis and its authorized agents to align with the change of sponsorship;
- Make administrative changes to align with Novartis processes and procedures;

As of **05-APR-16**:

**21** patients have received study treatment in **11** countries;

**07** patients have completed or discontinued study treatment.

The changes described in this amended protocol require Institutional Review Board (IRBs)/Independent Ethics Committee (IECs) approval prior to implementation.

A copy of this amended protocol will be sent to the IRB/IEC and Health Authorities (HAs).

The changes herein affect the Informed Consent and all sites are required to update and submit for approval, a revised Informed Consent that takes into account the change of study sponsorship described in the protocol amendment.

Upon approval of this amendment, patients who have already been enrolled in the study will sign a new informed consent form indicating Novartis is the new study sponsor and continue the appropriate visit schedule.

## LIST OF ABBREVIATIONS

β-hCG	Beta-human chorionic gonadotropin
AE	Adverse Event
AI	Adriamycin (doxorubicin) and ifosfamide
ALT	Alanine aminotransferase
AML	Acute myeloid leukemia
AST	Aspartate aminotransferase
ATS	All Treated Subjects
AUC(0-∞)	Area under the plasma concentration-time curve from zero (pre-dose) extrapolated to infinite time
BCRP	Breast cancer resistance protein
°C	Degrees Celsius
CIT	Chemotherapy-induced thrombocytopenia
CLD	Chronic liver disease
Cmax	Maximum plasma concentration
CPK	Creatine phosphokinase
CRO	Clinical Research Organization
CTCAE	Common terminology criteria for adverse events
CV	Cardiovascular
eCRF	Electronic case report form
EU	European Union
°F	Degrees Fahrenheit
FDA	Food and Drug Administration
FSH	Follicle-stimulating hormone
GCP	Good clinical practice
Gi/L	Giga units per liter
GSK	GlaxoSmithKline
HCV	Hepatitis C virus
HDPE	High density polyethylene
HMG-CoA	3-hydroxy-3-methyl-glutaryl-CoA reductase
HORT	Hematology/oncology related thrombocytopenia
HPLC	High performance liquid chromatography
HRT	Hormone replacement therapy
IB	Investigators brochure
ICH	International conference on harmonisation
IDSL	Integrated data standards library
IEC	Independent ethics committee
INR	International normalised ratio
IRB	Institutional review board
ITP	Idiopathic thrombocytopenic purpura
IVRS	Interactive voice response system
LDH	Lactate dehydrogenase
LSLV	Last subject's last visit
MDS	Myelodysplastic syndrome
MedDRA	Medical dictionary for regulatory authorities

MSDS	Material safety data sheet
NCI	National institutes of health
OATP1B1	Organic anion transporting polypeptide
OS	Overall Survival
PBO	Placebo
PCR	Polymerase chain reaction
PfOS	Powder for oral suspension
PK	Pharmacokinetic
RAP	Reporting and analysis plan
RMP	Risk management plan
RNA	Ribonucleic acid
SAE	Serious adverse event
SOC	Standard of care
SOP	Standard operating procedure
SPM	Study procedures manual
SVR	Sustained virological response
TPO	Thrombopoietin
TPO-R	Thrombopoietin receptor
TRALI	Transfusion-related acute lung injury
ULN	Upper limit of normal
US	United States

## PROTOCOL SUMMARY

### Rationale

Eltrombopag is an orally bioavailable, small molecule, thrombopoietin receptor TPO-R agonist that stimulates platelet production by a mechanism similar, but not identical to endogenous thrombopoietin (TPO). Eltrombopag has been approved in more than 90 countries including the United States (US) and the European Union (EU) for the treatment of chronic idiopathic thrombocytopenic purpura (ITP) and in November 2012 was approved in the US for the treatment of thrombocytopenia in patients with chronic hepatitis C. This Phase IV, multicenter, non-randomized, open-label rollover study will provide continued access to eltrombopag to subjects who are currently participating in a Novartis sponsored investigational study with eltrombopag (i.e. parent study such as TRC114968/ASPIRE or TRA105325/EXTEND), and are receiving clinical benefit without unacceptable toxicity.

### Objective

The objective of this study is to provide continuing treatment with eltrombopag for subjects who are currently participating in a Novartis sponsored investigational study of eltrombopag (parent study) and to collect long term safety data.

### Study Design

This Phase IV, multicenter, non-randomized, open-label, uncontrolled, rollover study is designed to provide continued access to eltrombopag to subjects who are currently participating in a Novartis sponsored investigational study of eltrombopag (**parent study**), and are receiving clinical benefit without unacceptable toxicity. Subjects will be enrolled into the appropriate cohort based upon the disease under study in their parent study (e.g. myelodysplastic syndrome (MDS), acute myeloid leukemia (AML), idiopathic thrombocytopenic purpura (ITP) etc). Enrollment into this study will be dependent upon the investigator's agreement to participate in this study. It is estimated that approximately 100 subjects will be enrolled. Instructions for the dose and dose adjustments throughout the duration of the study are described in Section 5.3 and Section 5.4 respectively. Subjects may continue treatment in this rollover study until they are no longer receiving clinical benefit, develop an unacceptable toxicity, withdraw consent, enroll into another interventional study, or until another mechanism is available for the subject to receive eltrombopag such as compassionate use, named patient program, commercially available for the appropriate indication, etc. Subjects participating in Investigator Sponsored Studies will not be eligible to participate in this study.

### Study Assessments

Safety will be evaluated through physical exams, clinical laboratory tests, and monitoring of adverse events as described in the Time and Events table. Additional safety assessments may be done as per standard of care (SOC) and/or when medically indicated.

Assessment of clinical benefit will be performed throughout the study using local SOC as determined by the investigator. Only subjects considered by the investigator to be receiving clinical benefit and without unacceptable toxicity may continue on study treatment.

## **1. INTRODUCTION**

### **1.1. Background**

Eltrombopag is an orally bioavailable, small molecule, thrombopoietin receptor (TPO-R) agonist. Eltrombopag functions in a similar manner to endogenous thrombopoietin (TPO), inducing proliferation and differentiation of megakaryocytes from bone marrow progenitors cells. Administration of eltrombopag in healthy adult subjects and in thrombocytopenic humans has resulted in a dose-dependent increase in platelet counts. Therefore, eltrombopag may be beneficial in medical disorders associated with thrombocytopenia.

The clinical consequences of thrombocytopenia include petechiae, bruising, and mucosal bleeding. Severe thrombocytopenia may be associated with morbidity and mortality due to bleeding, the most severe of which is intracerebral hemorrhage. Thrombocytopenia is a frequent finding in several medical disorders, including chronic idiopathic thrombocytopenic purpura (ITP), chronic liver disease (CLD), cancer and/or its treatments.

As of May 30 2013, Eltrombopag has been approved in more than 90 countries including the United States (US) and the European Union (EU) for the treatment of chronic ITP. The use of eltrombopag for the treatment of hepatitis C virus (HCV)-related thrombocytopenia has been recently approved in the United States (November 2012).

Eltrombopag is being developed for the treatment of a variety of additional medical disorders associated with thrombocytopenia, including myelodysplastic syndromes (MDS) and acute myeloid leukemia (AML) [GlaxoSmithKline Document Number UM2005/00217/08].

The safety profile of eltrombopag has been evaluated in 24 completed, concluded or ongoing Novartis-sponsored clinical studies: eleven studies of subjects with ITP, including 2 in pediatric subjects, 7 studies of subjects with CLD related thrombocytopenia (including 5 studies in HCV related thrombocytopenia), 5 studies for MDS/AML and 1 observational study for evaluation of ocular safety.

Please refer to the current version of the Investigator's Brochure (IB) for further information regarding pre-clinical and clinical studies [GlaxoSmithKline Document Number UM2005/00217/08].

#### **1.1.1. Chronic Idiopathic Thrombocytopenic Purpura Clinical Studies**

The eltrombopag adult ITP clinical program consists of a total of 9 studies. Eltrombopag has a well-defined safety profile with consistent findings across all ITP studies irrespective of treatment duration. Eltrombopag was well-tolerated across the ITP program. In placebo-controlled studies conducted globally, similar overall incidences of adverse events (AE), serious adverse events (SAE), and AEs leading to discontinuation from study medication were seen in the placebo (PBO) arms versus eltrombopag arms.

The ITP clinical studies have consistently demonstrated that eltrombopag raises platelet counts rapidly (within 1-2 weeks) and maintains platelet count elevations during therapy, regardless of splenectomy status, use of baseline concomitant ITP medication or baseline platelet counts. Bleeding symptoms were significantly reduced compared to placebo and during long-term treatment with eltrombopag; subjects were also able to reduce the use of concomitant ITP medications (predominantly corticosteroids) and required less rescue medication compared to placebo-treated subjects.

Eltrombopag is also being evaluated in pediatric patients with chronic ITP in 2 ongoing, double-blind placebo-controlled studies. Refer to Investigator's Brochure for Eltrombopag for available data from the pediatric studies [GlaxoSmithKline Document Number UM2005/00217/08].

### **1.1.2. Hepatitis C-Associated Thrombocytopenia Clinical Studies**

The pooled data from two Phase III studies (TPL103922/ENABLE 1 and TPL108390/ENABLE 2) in subjects with HCV-related thrombocytopenia demonstrates that eltrombopag treatment increased platelet counts in thrombocytopenic subjects with HCV infection to a level sufficient to allow initiation and maintenance of antiviral therapy for subjects who would otherwise be ineligible or poor candidates for peginterferon-based antiviral therapy. Therapy with peginterferon and ribavirin plus eltrombopag enabled 21% of patients to achieve sustained virological response (SVR); 13% of subjects in the control arm (which also included eltrombopag during the open label phase of the study) achieved an SVR. The results were statistically significant [GlaxoSmithKline Document Number UM2005/00217/08].

The AE profile of the eltrombopag treatment arm was consistent with a cirrhotic HCV patient population undergoing interferon-based antiviral therapy. Thromboembolic events and events suggestive of hepatic decompensation occurred more frequently in the eltrombopag arm. Hepatic decompensation is a known complication of interferon based antiviral therapy in patients with advanced fibrosis and cirrhosis.

Please refer to the current version of the Investigator's Brochure (IB) for further information regarding pre-clinical and clinical studies [GlaxoSmithKline Document Number UM2005/00217/08].

### **1.1.3. Hematology/Oncology Related Thrombocytopenia (HORT) Clinical Studies**

The HORT clinical program is investigating eltrombopag to treat thrombocytopenia associated with cancer and/or its treatments and includes chemotherapy-induced thrombocytopenia (CIT) and thrombocytopenia associated with hematologic malignancies. Thrombocytopenia is a significant problem for patients with malignancies and can be life-threatening. The etiology of thrombocytopenia depends on the specific type and location of the malignancy, and may encompass an autoimmune component, the presence of splenomegaly and/or prior and current treatments [GlaxoSmithKline Document Number UM2005/00217/08].

In the completed Phase II study, SB-497115/003, treatment with eltrombopag at 3 different dose levels after carboplatin/paclitaxel did not increase the severity of clinically meaningful side effects compared to treatment with placebo in subjects with cancer. The reported toxicities were consistent with the reported side effect profile of eltrombopag in other studies or the known toxicities of the carboplatin/paclitaxel combination. Eltrombopag 50 mg, 75 mg, and 100 mg, when given for 10 days after chemotherapy, failed to meet the study-defined primary endpoint of change in platelet count in Cycle 2 (measured by the difference in the platelet count from Day 1 in Cycle 2 to platelet nadir in Cycle 2), compared with placebo. However, mean platelet counts in the eltrombopag groups began to rise starting between Day 8 and Day 11, and continued to rise through Day 18 (post-nadir period). This same platelet count rise was not observed in the subjects receiving placebo. These results suggest that the tested schedule of administration (and possibly dose) in this study were likely not optimal for this subject population and chemotherapy regimen [GlaxoSmithKline Document Number UM2005/00217/08].

A completed Phase I (TRC105499) study in subjects receiving adriamycin (doxorubicin) and ifosfamide (AI) treatment for locally advanced soft tissue sarcoma, reported toxicities were consistent with the reported side effect profile of eltrombopag in other studies or the known toxicities of the AI combination [GlaxoSmithKline Document Number UM2005/00217/08].

In a completed Phase I/II study (PMA112509) in subjects with advanced MDS/AML reported AEs were consistent with those expected for the disease under study and with those expected during treatment with eltrombopag. No significant differences in post-baseline bone marrow blast percentages were observed for eltrombopag compared to placebo-treated subjects [GlaxoSmithKline Document Number UM2005/00217/08]. Platelet transfusion independence for  $\geq 8$  weeks was reported for 38% of eltrombopag and 21% of placebo subjects. Grade 3 or greater hemorrhages were reported in 16% of eltrombopag subjects compared to 26% of placebo subjects. More eltrombopag subjects started antileukemic/palliative treatment during the study (41%) compared to placebo subjects (32%). Median overall survival OS was 27 weeks for eltrombopag versus 15.7 weeks for PBO (hazard ratio=0.71,  $P=0.1931$ ).

TRC114968/ASPIRE study is a three-part (Part 1: open-label, Part 2: randomized, double-blind, Part 3: open-label extension), multi-center study to evaluate the effect of eltrombopag in subjects with MDS or AML who have thrombocytopenia due to bone marrow insufficiency from their underlying disease or prior chemotherapy. The starting dose was 100 mg (50 mg for East Asians), with a maximum dose of 300 mg (150 mg for East Asians). Subject who enrolled in Part 1 received open-label eltrombopag while those who enrolled in Part 2 received either eltrombopag or matching placebo. After completing Part 1 or 2, subjects could receive open-label eltrombopag in Part 3 (open-label extension). The planned number of subjects for this study is 150.

## **1.2. Study Rationale**

This study will provide continued access of eltrombopag to subjects who are currently participating in a Novartis sponsored investigational study with eltrombopag (parent

study such as TRC114968/ASPIRE or TRA105325/EXTEND), and are receiving clinical benefit without unacceptable toxicity.

### **1.3. Benefit:Risk Assessment**

In chronic ITP, HCV associated thrombocytopenia, and hematology/oncology related thrombocytopenia studies so far, eltrombopag has been able to increase platelet counts with an acceptable safety profile. In the setting of procedures for liver disease (HCV studies), an imbalance in thromboembolic events was observed. Therefore, with the exception of procedures for liver disease, the benefit:risk of eltrombopag in the other studied disease areas so far remain positive. Summaries of findings from both clinical and non-clinical studies conducted with SB-497115 can be found in the GlaxoSmithKline IB and product label. The following sections outline the risk assessment and mitigation strategy for this protocol.

#### **1.3.1. Chronic Idiopathic Thrombocytopenic Purpura**

The safety profile of eltrombopag has been well documented in the approved indication of chronic idiopathic thrombocytopenic purpura (ITP) to increase platelet counts and reduce or prevent bleeding. Eltrombopag has a well-defined safety profile with consistent findings across all ITP studies irrespective of treatment duration. Eltrombopag was well-tolerated across the ITP program. In placebo-controlled studies conducted globally, similar overall incidences of AEs, SAEs, and AEs leading to discontinuation from study medication were seen in the placebo (PBO) arms versus eltrombopag arms.

The ITP clinical studies have consistently demonstrated that eltrombopag raises platelet counts rapidly (within 1-2 weeks) and maintains platelet count elevations during therapy, regardless of splenectomy status, use of baseline concomitant ITP medication or baseline platelet counts.

#### **1.3.2. Hepatitis C virus-related thrombocytopenia**

The use of eltrombopag for the treatment of hepatitis C virus (HCV) related thrombocytopenia has been recently approved in the United States (November 2012), and is still under regulatory review in the European Union.

The pooled data from two Phase III studies (TPL103922/ENABLE 1 and TPL108390/ENABLE 2) in subjects with HCV-related thrombocytopenia demonstrates that eltrombopag treatment increased platelet counts in thrombocytopenic subjects with HCV infection to a level sufficient to allow initiation and maintenance of antiviral therapy for subjects who would otherwise be ineligible or poor candidates for peginterferon-based antiviral therapy.

The AE profile of the eltrombopag-containing treatment arm was consistent with a cirrhotic HCV patient population undergoing interferon-based antiviral therapy. Thromboembolic events and events suggestive of hepatic decompensation occurred more frequently in the eltrombopag arm. Hepatic decompensation is a known complication of interferon based antiviral therapy in subjects with advanced fibrosis and cirrhosis.

### **1.3.3. Hematology/Oncology Related Thrombocytopenia (HORT) Clinical Studies**

In the HORT clinical program, eltrombopag continues to be developed as a treatment of thrombocytopenia associated with cancer and/or its treatments, including chemotherapy-induced thrombocytopenia (CIT) and thrombocytopenia associated with hematologic malignancies. The studies are ongoing and eltrombopag has been well tolerated in the HORT indication to date.

### **1.3.4. Post Marketing**

Eltrombopag was first approved for marketing in the US on 20 November 2008 for the treatment of thrombocytopenia in patients with chronic immune (idiopathic) thrombocytopenic purpura and is currently available in 90 countries.

The data reported in the post marketing setting are consistent with the known safety profile of eltrombopag. Overall, there was no change in the nature, seriousness or frequency of reported events, based on the post marketing data. The benefit risk profile of eltrombopag for the treatment of chronic ITP continues to be favorable in the post marketing setting.

### **1.3.5. Risk Management**

Risk management strategies for eltrombopag are in place for patient safety.

Novartis has a robust risk management plan (RMP) for eltrombopag where the presentation and management of risks are conveyed. Safety data continue to be collected and analyzed for eltrombopag since the initial approval of PROMACTA™ (eltrombopag) in the United States in 2008 and the subsequent approval of REVOLADE™ (eltrombopag) in the EU in 2010.

A comprehensive Risk Management Plan (RMP) is in place for eltrombopag. Identified risks described in the RMP include hepatobiliary laboratory abnormalities, thromboembolic events, post therapy reoccurrence of thrombocytopenia, and hepatic decompensation in patients with hepatitis C. Potential risks in the RMP include increased bone marrow reticulin formation, cataract, renal tubular toxicity, and photosensitivity.

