- Only in those with underlying chronic hepatitis B at study entry (identified by positive hepatitis B surface antigen): quantitative hepatitis B DNA and hepatitis delta antibody. **NOTE:** if hepatitis delta antibody assay cannot be performed, it can be replaced with a polymerase chain reaction (PCR) of hepatitis D RNA virus (where needed [Le Gal, 2005]).
- Liver imaging (ultrasound, magnetic resonance, or computerized tomography) to evaluate liver disease.

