### **5.10.2. Liver Chemistry Monitoring Criteria**

For subjects with ALT  $\geq 3$ xULN **but**  $< 5$ xULN **and** bilirubin  $< 2$ xULN, without hepatitis symptoms or rash, and who can be monitored weekly for 4 weeks, the following actions should be taken

- Notify the Novartis Medical Lead within 24 hours of learning of the abnormality to discuss subject safety.
- Continue study treatment
- Must return weekly for repeat liver chemistries (ALT, AST, alkaline phosphatase, bilirubin) until they resolve, stabilize or return to within baseline values
- If at any time these subjects meet the liver chemistry stopping criteria 1 - 5, proceed as described above
- If, after 4 weeks of monitoring, ALT  $< 3$ xULN and bilirubin  $< 2$ xULN, monitor subjects twice monthly until liver chemistries normalize or return to within baseline values.

Refer to Appendix 2 Liver Chemistry Monitoring, Interruption, Stopping and Follow-up Criteria for algorithm of liver chemistry monitoring, stopping and follow up criteria

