## 2.7.3 Laboratory data

Laboratory values will be converted to the international system of units (SI). CTCAE Grade 0 will be assigned for all non-missing values not graded as 1 or higher. Grade 5 will not be used. For laboratory tests where grades are not defined by CTCAE version 4.03, results will be categorized as low/normal/high based on laboratory normal ranges.

The following summaries will be provided. Note that except for baseline value only on-treatment values will be used in summaries.

- Shift tables using CTCAE grades to compare baseline to the worst on-treatment value for platelets, hemoglobin and white blood cells (WBCs).
- Summary table for platelet counts over time.

Listings of all available laboratory data (hematology, biochemistry, urinalysis, coagulation, pregnancy test etc.) will be provided showing the corresponding CTCAE grades, if applicable, and the classifications relative to the laboratory normal ranges. Values measured outside of on-treatment period will be flagged.

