## Liver function parameters

Liver function parameters of interest are total bilirubin (TBL), alanine aminotransferase (ALT), aspartate aminotransferase (AST) and alkaline phosphatase (ALP).

The number (%) of patients with worst on-treatment values will be summarized. For single lab parameter lines (e.g. AST > 3xULN) the worst value post-baseline is considered. For combination of various parameters (e.g. ALT or AST > 3xULN & TBL > 2xULN & ALP < 2xULN) the lab values need to be from the same assessment (concurrent measurements).

Listings of all available liver event data will be provided. Values measured outside of on-treatment period will be flagged.

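### The SAP's only specified summary of liver tests ignores baseline, so a value already above a row's cut-off at the Transition Visit is counted like a new one

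*Protocol*

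**What the plan says.** Protocol 1.3.5 (Risk Management) names the hepatobiliary item first of four: "Identified risks described in the RMP include hepatobiliary laboratory abnormalities", followed by thromboembolic events, return of thrombocytopenia after therapy, and hepatic decompensation in hepatitis C.

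SAP 2.7.3, under Liver function parameters, sets the summary: "The number (%) of patients with worst on-treatment values will be summarized". Single-parameter rows follow this rule: "For single lab parameter lines (e.g. AST > 3xULN) the worst value post-baseline is considered". Rows that combine parameters add only a timing condition: "the lab values need to be from the same assessment (concurrent measurements". Neither rule mentions the subject's baseline.

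The same SAP section treats hematology differently: "Shift tables using CTCAE grades to compare baseline to the worst on-treatment value for platelets, hemoglobin and white blood cells (WBCs". No liver parameter has a shift table.

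Protocol 10.3.4.1.2 planned a summary of hematology and clinical chemistry by CTCAE grade at each scheduled assessment. SAP 2.7.3 contains no such summary for chemistry. SAP Section 4, which lists changes to the protocol's analyses, does not mention the omission. The SAP's document history records that some laboratory analyses were removed but does not say which.

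The baseline data exist. SAP 2.1.1 defines baseline as the Transition Visit result. Protocol 8.1 and Table 5 require ALT, AST and total bilirubin at that visit.

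**The concern.** Every subject comes from another eltrombopag study, so some liver tests may already be raised when the rollover starts. Protocol 4.1.2 and 4.1.3 set no numerical limit on ALT, AST or bilirubin at entry. The protocol also allows for abnormal starting values: monitoring under 5.10.2 runs "until they resolve, stabilize or return to within baseline values", and one follow-up test in 5.10.1.1 is required "Only in those with underlying chronic hepatitis B at study entry".

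The SAP's adverse event tables count only events that began or got worse on treatment, and three hematology parameters are compared with baseline. The liver table does neither. A reader who wants to know whether liver abnormalities arose during the rollover cannot tell from this table. With so few subjects, one carried-in value could be the whole content of a row.

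**Working it through.** The plan gives no figure for this table, so there is none to reproduce. The check applies the SAP's counting rule to hypothetical subjects and then sizes the weight of one subject.

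**Step 1. The counting rule.** The SAP counts a subject if the worst post-baseline value exceeds the row's cut-off. The comparison rule also requires the baseline to be at or below the cut-off. The SAP gives cut-offs only as examples, so single rows for ALT above 3xULN and total bilirubin above 2xULN are assumed.

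| Hypothetical subject (xULN) | Row | SAP rule | Baseline also required at or below cut-off |
|---|---|---|---|
| Bilirubin 2.4, unchanged | >2 | counted | not counted |
| ALT 3.5, unchanged | >3 | counted | not counted |
| ALT 1.5, unchanged | >3 | not counted | not counted |
| ALT 3.5, falls to 1.0 | >3 | not counted | not counted |
| ALT 1.0, rises to 3.5 | >3 | counted | counted |
| ALT 3.5, rises to 9 | >3 | counted | not counted |

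The first two rows show the gap. The third shows that a stable elevation below the cut-off is not affected. The last shows that dropping subjects with a raised baseline would be the wrong remedy, because it would hide real worsening.

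**Step 2. Which parameter is exposed.** Protocol 5.10.1 has five liver stopping criteria, and each involves ALT of at least 3xULN. One of them is ALT at that level persisting for 4 weeks or more. A carried-in ALT above 3xULN should therefore not continue unchanged for long, although a single on-treatment value is enough for it to be counted. Bilirubin appears only in combination with ALT. An isolated bilirubin above 2xULN could thus be carried through the whole treatment period without meeting any of the five.

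**Step 3. Weight of one subject.** SAP Section 1 gives 22 subjects, and SAP 2.7 presents safety by cohort. The cohort split is not given.

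- Pooled: 1/22 = 4.5% (exact 95% interval 0.1 to 22.8%).
- Assumed cohort of 14: 1/14 = 7.1%.
- Assumed cohort of 8: 1/8 = 12.5%.
- Assumed cohort of 5, as a more uneven split: 1/5 = 20.0%.

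In general, k subjects who start and stay above the cut-off put a floor of k/n under the row.

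**Step 4. Chance that it arises.** The share p entering above a cut-off is not in the documents. With 22 subjects, the chance of at least one is 1 − (1 − p)^22:

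- p = 5%: expected number 22 × 0.05 = 1.1; chance 68%.
- p = 10%: expected number 2.2; chance 90%.
- p = 20%: expected number 4.4; chance 99%.

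These values of p are assumptions, chosen to show the range.

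**The case against.** The case against is substantial, and much of it stands.

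- **The table reports what it says it reports.** It is labelled as worst on-treatment value, and absolute multiples of ULN match the protocol's stopping thresholds. A reader might infer that the planned percentages are wrong. They are not; they would mislead only if read as new abnormalities.
- **A reader might infer that any raised ALT or bilirubin at entry is counted.** Only values above a row's cut-off are.
- **A reader might picture an ALT just above 3xULN carried unchanged through the study.** The 4-week criterion works against that, and such a subject would be an on-study liver event by the protocol's own definition. Protocol 4.2.1 and 5.10.2 also differ on whether treatment continues in the 5.10.2 range. Those passages must be reconciled, but this point does not depend on the outcome.
- **A reader might infer that such subjects were enrolled.** The documents do not show this. Entry requires no unacceptable toxicity in the investigator's judgement, and subjects permanently discontinued under parent-study criteria are excluded. The baseline and hepatitis B wording is conditional instruction, not evidence about who entered.
- **Other outputs partly cover the gap.** Adverse event tables are restricted to treatment-emergent events, adverse events of special interest are tabulated, and all laboratory values are listed, including pre-treatment ones. With 22 subjects, a reader can check each case.
- **Table shells were not available.** The SAP refers to standard safety outputs that are not supplied, and SAP 2.1.1 allows baseline data where suitable. A shell might include baseline, but the SAP text does not ask for it.

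What remains is that no specified summary compares liver tests with baseline. Listings let a reader work around this but do not repair the summary. The omitted by-visit grade summary would have shown starting and later distributions, although without linking them within subjects.

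**Conclusion.** The gap is real and modest. As specified, the liver table cannot separate values carried in from values that arose during the rollover. It is an omission in the analysis specification, not an error in a stated number, and Protocol 1.3.5 only shows why it matters.

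One subject who starts and stays above a cut-off adds 4.5 points to a pooled row, or 7.1 to 12.5 points in assumed cohorts of 14 to 8. These sizes rest on the assumed split and on at least one such subject existing. The absence of a baseline comparison rests on neither.

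The documents do not support reading every carried-in elevation as unrelated to the drug. Baseline is measured after eltrombopag in the parent study, so a raised starting value may itself be a drug effect.

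**What to change.** In SAP 2.7.3, under Liver function parameters:

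1. Add, by cohort, a table of worst on-treatment category by baseline category for ALT, AST and total bilirubin. Use the Transition Visit baseline, the same cut-offs as the existing rows, and a missing-baseline category. Alkaline phosphatase is left out because Table 5 does not schedule it.
2. Keep subjects with a raised baseline in the table, so that worsening from a raised start stays visible. New exceedances can then be read from the cells whose baseline is at or below the cut-off.
3. Keep the existing absolute-threshold rows unchanged.
4. Add a footnote that baseline follows parent-study eltrombopag, so a carried-in elevation may itself be a drug effect.
5. State in SAP Section 4 that the by-visit, by-grade chemistry summary of Protocol 10.3.4.1.2 is not produced, or reinstate it.

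The cost is SAP wording and one extra table shell. It needs no new assessments and changes no existing count.
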